## **Main Outcome Measures**

The demographic data of the participants were recorded on a personal information form. Pain intensity and fatigue were evaluated by the Visual Analogue Scale (VAS), kinesiophobia by the Tampa Scale of Kinesiophobia (TSK), depression by the Beck Depression Inventory (BDI), physical activity level by the International Physical Activity Questionnaire (IPAQ) Short Form, functional status in patients with FS by the Fibromyalgia Impact Questionnaire (FIQ), and neck pain-related disability in the neck pain group by the Neck Pain Disability Index (NPDI). The details of the implementation of the instruments are as follows: Visual Analog Scale (VAS) for the Evaluation of Pain and Fatigue For this evaluation, the patient is asked to mark his/her severity of pain and fatigue on a horizontal 10-cm line with number 0 on one end representing “no pain or no fatigue” and number 10 on the other end indicating “very severe pain or very severe fatigue” (14, 15). Tampa Scale of Kinesiophobia (TSK) Based on a four-point Likert type, this scale contains 17 items that evaluate fear and anxiety related to physical activity. A total score of greater than 37 is accepted as statistically significant and interpreted as a high level of kinesiophobia. The validity and reliability analysis of the Turkish version of TSK was undertaken by Yilmaz et al. (16). Beck Depression Inventory (BDI) This is a 21-item questionnaire that investigates the characteristic attitudes and symptoms of depression. A score of 10 or higher indicates depression (17). International Physical Activity Questionnaire (IPAQ) Short Form IPAQ consists of seven items that measure the duration of the participants’ physical activity, walking and sitting within the last seven days in the MET-min/week unit (18). Fibromyalgia Impact Questionnaire (FIQ) FIQ aims to evaluate the arthritis symptoms and functional status of patients with FS through 21 questions that inquire about physical functions, work-related situations, depression, anxiety, waking up tired, pain, stiffness, and fatigue. The validity and reliability of the Turkish version of FIQ was tested by Ediz et al. (19). Neck Pain Disability Index (NPDI) This index consists of 20 questions that assess severity of neck pain and the extent to which the pain affects the social, professional and daily activities of patients (20).

## **Statistical Analysis**

Statistical analysis was performed using the Statistical Package for the Social Sciences (SPSS) v. 15.0. Descriptive statistics were given as mean  $\pm$  standard deviation (SD) for

variables with normal distribution, and frequency tables for ordinal and categorical variables. We chose to conduct the Kolmogorov-Smirnov test for the normalization analysis. The MannWhitney U test was employed for paired comparisons of numerical sociodemographic data, chi-square test for the paired comparison of categorical sociodemographic data and the comparison of sociodemographic data (except age and disease duration) between three groups, and one-way analysis of variance (ANOVA) for the comparison of age and disease duration between the three groups. Before conducting one-way ANOVA, the Levene test was performed to test the homogeneity of variance. Since the result of this test was  $p > 0.05$  for VAS-fatigue, TSK and BDI, the Tukey test was employed for post hoc analysis. For VASpain and FIQ that produced  $p < 0.05$  in the Levene test, the Games-Howell post hoc test was preferred. Spearman's correlation analysis was undertaken individually for each group. The level of statistical significance was accepted as  $p < 0.05$

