## **Evaluation of Kinesiophobia and Physical Activity Levels in Patients with Fibromyalgia Syndrome and Chronic Neck Pain**

### **ABSTRACT**

**Introduction:** Kinesiophobia which is described as fear of movement reduces physical activity levels and increases the risk of chronic pain. Kinesiophobia has not been studied in detail in patients with fibromyalgia syndrome and chronic neck pain.

**Objective:** To evaluate pain, kinesiophobia, physical activity, depression, disease severity, and fatigue in patients with fibromyalgia syndrome or chronic neck pain and healthy controls.

**Design:** Cross-sectional study. Setting: Tertiary Health Care Center, Aksaray, Turkey  
Participants: 30 patients with fibromyalgia syndrome (Group 1), 30 patients with chronic neck pain (Group 2), and 30 healthy individuals (Group 3) were included.

**Main Outcome Measures:** Outcome measures were Visual Analogue Scale (VAS)-pain and fatigue, Tampa Scale of Kinesiophobia (TSK), Beck Depression Inventory (BDI), International Physical Activity Questionnaire (IPAQ) Short Form, Fibromyalgia Impact Questionnaire (FIQ), Neck Pain Disability Index (NPDI).

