
## METHODS

### Study Design

We assessed pain intensity, kinesiophobia, fatigue, depression, physical activity level and disability in patients with FS and CNP, and healthy individuals in this cross-sectional study. The patients were recruited from a physical medicine and rehabilitation outpatients clinic of Aksaray University Training and Research Hospital, Aksaray, Turkey. The healthy control group was consisting of doctors, nurses, medical secretaries who work in Aksaray University Training and Research Hospital, and patient care providers that have no pain and additional diseases. Following the Helsinki Declaration, our study was approved by the Ethics Committee of Aksaray University Training and Research Hospital

(26.9.18, reference number: 2018/155) and written informed consent was obtained from all the participants.

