## **Participants**

Thirty patients with a diagnosis of FS according to the 2016 revised ACR FS diagnostic criteria and a disease duration of longer than three months; 30 patients with CNP lasting for more than three months, and 30 healthy controls without pain or additional disease were included in the study that was conducted between October 2018 and December 2018. All the participants were aged 18 to 65 years. The exclusion criteria were malignancy, systemic infectious and rheumatic diseases, history of operation, having received physical therapy or intra-articular or intra-ligamentary injection within the last three months, previous diagnosis of a psychological or cognitive disorder, and history of pregnancy.

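### Disease duration is assigned to a three-group ANOVA, although the healthy control group has no disease duration and its handling is not stated

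*Combined protocol and SAP*

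**What the plan says.** The Statistical Analysis section assigns "one-way analysis of variance (ANOVA) for the comparison of age and disease duration between the three groups". Earlier in the same sentence the chi-square test is given for "the comparison of sociodemographic data (except age and disease duration) between three groups", so duration is again grouped with age and directed to the ANOVA. The sentence also says that the Mann-Whitney U "test was employed for paired comparisons of numerical sociodemographic data", without naming any variable.

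The Abstract identifies the groups: "30 patients with fibromyalgia syndrome (Group 1), 30 patients with chronic neck pain (Group 2), and 30 healthy individuals (Group 3) were included". Participants gives a duration criterion for the two patient groups only: "a disease duration of longer than three months; 30 patients with CNP lasting for more than three months". It describes the third group thus: "30 healthy controls without pain or additional disease were included in the study". Study Design agrees, listing hospital staff and "patient care providers that have no pain and additional diseases".

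No section says what value, if any, a control carried for disease duration.

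**The concern.** Age can be compared across all three groups. Disease duration cannot: it is undefined for the controls by the way they were selected. A three-group test of it needs a value for each of those 30 people, and any such value is invented. If the controls simply drop out, the test is no longer a three-group test.

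A reader who meets a three-group p-value for disease duration therefore cannot tell what it measures. It may compare the two patient groups, or it may only confirm that patients have a disease and controls do not. The useful question about this variable is whether the FS and CNP patients were ill for similar lengths of time, and only a two-group comparison answers it.

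**Working it through.** The documents report no duration data, standard deviation or test result, so there is no figure to reproduce. The main point follows from setting the sections side by side; the arithmetic shows how much the unstated handling matters.

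**Inputs from the documents**
- Three groups of 30: FS, CNP, healthy (Abstract).
- Duration above three months in FS and in CNP; no pain or disease in controls (Participants, Study Design).
- Significance level 0.05 (Statistical Analysis).

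**Inputs that are assumptions**
- FS and CNP durations come from one common distribution, gamma or lognormal, with mean *m* and coefficient of variation CV = SD/*m*.
- CV ranges from 0.5 to 3, because the documents give no SD.
- Controls are either all zero or all blank.

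**Step 1. Degrees of freedom.**
- Three groups: 3 − 1 = 2 and 90 − 3 = 87; critical F = 3.10.
- Controls blank: 2 − 1 = 1 and 60 − 2 = 58; critical F = 4.01.

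These are different tests, and the text does not say which was run.

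**Step 2. Controls zero, by hand.** Take sample means *m*, *m*, 0 and sample SDs CV·*m*, CV·*m*, 0. The grand mean is 2*m*/3.
- Between-group sum of squares: 30 × [(*m*/3)² + (*m*/3)² + (2*m*/3)²] = 30 × (6/9)*m*² = 20*m*². Mean square: 20*m*²/2 = 10*m*².
- Within-group mean square: (29 + 29) × CV²*m*²/87 = (2/3)CV²*m*².
- F = 10 / [(2/3)CV²] = 15/CV².

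This gives F = 60 at CV 0.5, 15 at CV 1, 6.67 at CV 1.5, 3.75 at CV 2 and 1.67 at CV 3. It passes 3.10 at CV = √(15/3.10) = 2.20. *m* cancels, so the mean duration does not matter here. All of F comes from the zeros, since FS and CNP were set equal.

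**Step 3. Controls zero, by simulation** (20,000 runs per cell). For CV 0.5 to 1.0 without a duration floor, the three-group ANOVA gives p < 0.05 in at least 99.98% of runs. For larger CVs, the percentage with p < 0.05 is:

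| CV | Gamma, no floor | Lognormal, no floor | Gamma, three-month floor | Lognormal, three-month floor |
|---|---|---|---|---|
| 1.5 | 99.9 | 98.3 | 99.6–99.8 | 98.2 |
| 2.0 | 91.8 | 93.4 | 91.8–92.3 | 93.9–94.3 |
| 2.5 | 64.4 | 87.1 | 67.0–72.3 | 87.6–89.6 |
| 3.0 | 37.8 | 80.6 | 40.2–52.9 | 81.5–86.0 |

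The floor columns enforce the entry criterion, hold the CV of total duration fixed, and span assumed mean durations of 15, 39 and 63 months. Rates at high CV exceed what Step 2 suggests because in skewed samples the observed CV usually falls below the population value.

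These are not type I error rates. With zero coding the three-group null hypothesis is false by construction. The rates show how far the p-value reflects who was eligible when FS and CNP do not differ at all.

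**Step 4. Controls blank.** The resulting two-group ANOVA gives p < 0.05 in 3.2–5.0% of runs over all 14 combinations of distribution and CV without the floor.

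**Step 5. The replacement test.** A Mann-Whitney U test of FS against CNP gives p < 0.05 in 4.5–5.1% over the same combinations.

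**The case against.** The strongest reply is that this is a slip of wording. Age and duration share one compressed clause; the reference to three groups may have been meant for age, with duration carried along. The second mention is in the same sentence and is not independent evidence that control values were analysed. If the controls' field was empty, they would drop out and the result would be sound. The Mann-Whitney test may also already cover the point: duration is treated as a numerical sociodemographic variable, and FS against CNP is its only possible pair. Finally, the large rejection rates all depend on zero coding, which no section supports, and the simulation without a floor generates ineligible patients. With an assumed mean of 36 months, about 42% of gamma draws at CV 2 and 63% at CV 3 fall below three months.

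Much of this stands. The innocent reading is possible, zero coding is only an assumption, and the Mann-Whitney test may have been applied to duration. At high CV the floor columns are the better guide; up to CV 2 they differ little from the others. What does not follow is that the text is adequate. It states three groups, a reader cannot confirm the charitable reading, and under that reading the label is still wrong. The two-group ANOVA also holds its level in these simulations, so the essential correction is restricting the comparison to the patients; the choice between the two tests is secondary.

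**Conclusion.** The concern holds, as a minor one. The stated three-group comparison of disease duration is wrong as written, because one group has no value for the variable. That conclusion rests on the text alone and needs no simulation.

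The consequence depends on an unstated choice. With blank controls there is no inflated error, only a mislabelled two-group test. With zero-coded controls, significance is nearly certain for CVs up to about 1.5 even when FS and CNP are identical, and becomes less certain above that.

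The reach is one background variable. The objective reads "To evaluate pain, kinesiophobia, physical activity, depression, disease severity, and fatigue in patients with fibromyalgia syndrome or chronic neck pain and healthy controls" and does not include duration. Main Outcome Measures does not list it, and the Statistical Analysis section names no adjusted model that uses it. Results for kinesiophobia, depression, fatigue and physical activity are untouched.

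**What to change.** Remove disease duration from the three-group ANOVA and from the exception in the chi-square clause. State that it is compared between FS and CNP only, with the Mann-Whitney U test the section already names, and show it as not applicable for the healthy group. Keep age in the three-group ANOVA.

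The study is described in the past tense, so the cost is one corrected sentence and one re-reported background variable. No new data are needed. The only loss is a three-group p-value that has no clear meaning.
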